Family-centred care (FCC) is, in fact, developmentally supportive care that helps develop bonding (12). Intermittent kangaroo mother, as a part of FCC, benefits from maternal-neonatal bonding (13). Similarly, the role of maternal involvement in pre-feeding sensorimotor stimulation is a hidden corner in research. To our knowledge, not even a single international or national study is available in this regard.

In resource-constrained setups with limited properly trained speech therapists and neonatal nurses, mothers can be involved in pre-feeding sensory motor stimulation after training and teaching to improve their feeding performance. Within this context, the current study aims to determine the following: 1) the maternal role in sensory-motor stimulation for oral feed establishment in preterm neonates, 2) determine the effect of sensory-motor stimulation offered by the mother on the onset of oral feeding, and 3) the efficiency of mother-mediated stimulation techniques on oral feeding compared to trained nurses.

Keywords

Prematurity sensory-motor stimulation oral feed establishment, feeding intervention

Material and methods

An interventional, prospective, randomized control trial was conducted after ethical approval from the Institutional Review Board of Fatima Memorial Hospital (FMH-07-2021-IRB-929-M). The authors confirm that this intervention's ongoing and related trials are registered in the ClinicalTrials.gov platform—accession number NCT05484726. The study protocol can be accessed at <https://www.clinicaltrials.gov/ct2/show/NCT05484726>.

Study hypothesised that preterm babies who receive sensory motor stimulation from their mothers as compared to trained nurses, are

- Start taking oral feed at the same time as compared to the control group
- Take the same amount of milk at the commencement of oral feeding
- Take milk with equal efficiency
- Not face more adverse effects

The study period spans 16 months, from March 2022 to July 2023, in the department of Neonatology, Fatima Memorial Hospital, Lahore. We enrolled all preterm neonates of gestation age 28 to 34 weeks who were admitted to NICU during the study period after seeking consent from parents or guardians. All these neonates were haemodynamically stable, established gavage feed, had no respiratory distress, no need for respiratory support except LFNC and did not receive any kind of analgesics at time of enrollment.

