However, all those neonates having major anomalies incompatible with life, major malformations, syndromic babies, cleft lip and palate, genetic disorders, haemodynamically unstable babies including IVH (grade III & IV), haemodynamically significant PDA (HsPDA) requiring antifailure therapy, NEC (stage II & III) or anemia requiring blood transfusion. All those neonates with adverse events including cough with choking, breath holding, choking, aspiration, tachycardia HR > 200/min, bradycardia HR < 100/min, apnea > 15 sec, tachypnea RR > 70/min while stimulation or feeding were excluded.

Protocol

Interventional Study Model: Factorial Assignment

- Maternal involvement in perioral sensory-motor stimulation be in three stages
 - Observer status
 - Performing under supervision
 - Independent
- Intervention period: 5 days as
 - Training phase (T): T1 and T2 (for mothers by the nurse)
 - Direct feeding phase (D): F1, 2, and 3 (oral feed was offered to neonate)
- Stimulation for 7 minutes and 15 minutes before feeding twice a day at 1100 and 1700 hrs.
- Two groups
 - Intervention group (G I): by mothers
 - Control group (G II): by staff nurses

Number of Arms: 2

Masking: Single (Care Provider)

The mothers, medical staff involved in general care, nursing staff involved in the intervention, and doctors conducting the assessment of oral feeding skills (OFS) were all blinded to allocation. The nursing staff was informed at the time of intervention that participating infants received either sensory motor stimulation or sham oral stimulation depending on group allocation.

Allocation

Randomization was done using a random Alloc Software environment. Gestation age-based stratification was done using 3 blocks design of 28 to 30, 30+1 to 32 & 32+1 to 34. Random allocation of neonates into the intervention or control groups by stratum using lottery method.

Blinding

The mothers, medical staff involved in general care, nursing staff involved in intervention and doctors conducting the assessment of oral feeding skills (OFS) were all blinded to allocation. The nursing staff was informed at the time of intervention that participating infants received either sensory motor stimulation or sham oral stimulation depending on group allocation.

Sample size

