The sample size was 46 (23 each in interventional and control groups) and calculated with a 95% confidence level, 10% margin of error and 5% level of significance by taking feeding-related problems as 40%. It was done by using openepi.com.

Initially only 46 neonates were enrolled in study. But later an immense maternal response was observed. Mothers were ready to learn and involve in sensory motor stimulation of their neonates. Hence, the final total study population size was 97 with 49 in experimental and 48 in control group.

Procedure of intervention

- The study intermediation was started not before 30 weeks of postmenstrual age when full gavage feeding was established with the addition of supplements.
- All mothers in this study was involved in gavage feeding before involvement in the procedure.
- Trained nurses taught details of sensory-motor stimulation to mothers in easily understandable languages (annexure 1 in (a) English and (b) Urdu). This procedure has been adapted from modified from PIOMI and Fucile (14,15).
- Stimulation was done for 7 minutes and at least 15 minutes before feeding twice daily at 1100 and 1700 hrs till full oral feed establishment (expected time 28 days chronological age)
- Oral feeding was offered using a bottle with a slow-flow nipple.
- Time monitoring for feeding was strictly followed
- Infants was fed for a maximum of 20 min, and feeding was discontinued early if adverse events occur.

Arms and intervention

- Study groups for sensory motor stimulation (5 minutes) + pacifier (2 minutes)
 - Intervention group (G1) : by mothers
 - Control group (G 2) : by staff nurses

Experimental: Intervention group (Group 1)

- Maternal involvement was done in three stages for the intervention group as
 - Observer status
 - T1: Nurses performing all steps while mother observer status
 - T2: Nurses perform all steps in front of the mother and a pacifier was offered by the mother
 - Performing under supervision
 - D1: Mother performs all steps and oral milk was offered by the nurse while the mother observes.
 - D2: Mother performing all steps and offering oral milk while the nurse is supervising

- Independent
 - D3: Mother performing all steps independently
- Study groups for sensory motor stimulation
 - Assigned intervention perioral sensory motor stimulation Step 1 - 6 over 5 minutes + pacifier 2 minutes for total duration of 7 minutes.

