 - Volume taken during the first 5 min (TV₅) out of total feed taken orally
 - Rate of transfer (RT) ml/min i.e., how long it neonate takes to finish oral feed.
 - Overall transfer (OT percent) volume taken/total volume prescribed. It shows trend towards oral feed establishment.
 - Proficiency (PRO percent) volume taken during the first 5 min/total volume prescribed.
 - SSB (Suck Swallow Breaths) coordination coordinated, developed pattern of suck swallow and breathe. It is a subjective assessment.

Statistical analysis

The statistical software IBM SPSS Statistics version 21 (SPSS, Chicago, IL) was used for the statistical analysis of the data. Appropriate bivariate analysis was performed to identify the unadjusted differences between the cases and controls. Categorical variables were expressed as frequencies and percentages. According to Shapiro Wilk test all continuous variables were asymmetrically distributed. Mann–Whitney U test was used for nonparametric continuous variables and were described as medians and inter quartile range (IQR). Fisher exact/Chi square test was used to compare categorical variables. Mann-Whitney test was used to compare continuous variables. The p-value of < 0.05 was taken as statistically significant.

Results

During the research period, 1009 newborns were admitted to the Neonatal Intensive Care Unit (NICU). Among them, 142 were born prematurely, with gestational ages falling between 28 and 34 weeks. Out of the preterm neonates, a total of 130 were eligible for the study, as 12 had to be excluded for various reasons. These exclusions included 2 cases where mothers experienced serious postnatal complications, 1 instance of parental refusal to participate, 1 case with incomplete data, and 8 cases that did not meet the inclusion criteria due to different reasons such as syndromic features, cleft lip and palate, suspected inborn error of metabolism (IEM), intraventricular hemorrhage (grade IV), and hemodynamically significant patent ductus arteriosus (HsPDA). Consequently, 130 neonates were included in the study and randomly assigned, with 65 in each group for intervention and control. Sensory motor stimulation (SMS) was administered to 107 of these neonates, and the study was completed with 97 neonates (as illustrated in Figure 1).

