The sociodemographic and clinical characteristics of both mothers and neonates are shown in Table 1. There were no statistically significant differences between groups regarding maternal age, gravidity, education, previous preterm neonates, job status and pregnancy related issues (hypertensive disorder of pregnancy, gestational diabetes, and anemia). Similarly, neonatal characteristics regarding gender, mode of delivery, gestation age, birth weight, weight for gestation age, place of delivery, need and duration of invasive mechanical ventilation (IMV), non

invasive ventilation (NIV) and low flow nasal cannula (LFNC), apnea, RDS, use of caffeine, HsPDA, NEC stage 1, feed intolerance, sepsis, and seizures. (Table 1).

There was also no significant difference in feeding characteristics. The feeding characteristics assessed were postmenstrual (PMA), chronological (ChA) age, and weight at enrollment, time to full gavage feed establishment, amount of milk feed advised for each feed and day on D1, D2, D3, D5, D7 and D14. (Table 2).

Table 3 provides an overview of both the primary and secondary outcomes observed in both study groups. When examining the primary outcome measures, there were no significant differences observed in terms of the time it took to establish full oral feeding, adverse events, or the effectiveness observed during oral assessments. The findings indicate that neonates in the experimental group demonstrated oral feeding skills that were comparable to those in the control group. These skills were measured in terms of volume (both total and during the initial 5 minutes of feeding), feeding rate, overall transfer, proficiency, and the coordination of suck, swallow, and breath (Table 3).

References:

1. da Rosa Pereira K, Levy DS, Procianoy RS, Silveira RC. Impact of a pre-feeding oral stimulation program on first feed attempt in preterm infants: Double-blind controlled clinical trial. *PLoS One*. 2020 Sep 9;15(9):e0237915. doi: 10.1371/journal.pone.0237915. PMID: 32903261; PMCID: PMC7480839.

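### Outcomes are compared in 97 of the 130 randomised neonates, with no all-randomised analysis or missing-data method, so the finding of comparable results holds for completers only

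*Combined protocol and SAP*

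**What the plan says.** - **Results, participant flow.** "130 neonates were included in the study and randomly assigned, with 65 in each group". Then: "Sensory motor stimulation (SMS) was administered to 107 of these neonates, and the study was completed with 97 neonates".
- **Sample size.** "the final total study population size was 97 with 49 in experimental and 48 in control group". Tables 1 to 3 carry the same 49 and 48 in their column heads.
- **Statistical analysis.** "Appropriate bivariate analysis was performed to identify the unadjusted differences between the cases and controls". The section goes on to software, summary measures, tests and a significance threshold. It does not say who is analysed or what happens to unobserved outcomes.
- **Results, conclusion.** Experimental-group neonates "demonstrated oral feeding skills that were comparable to those in the control group". No significant difference is reported in time to full oral feeding, adverse events or efficacy.
- **Material and methods, exclusions.** Neonates with choking, aspiration, HR above 200 or below 100, "apnea > 15 sec, tachypnea RR > 70/min while stimulation or feeding were excluded".
- **Procedure of intervention.** A feed was stopped early if an adverse event occurred.
- **Primary Outcome Measure, adverse outcomes.** Non-life-threatening events, with bands HR 180-200, HR 120-100 and RR 60-70, monitored in every neonate from D1.

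**The concern.** The trial hypothesises sameness: equal start of oral feeding, equal volume, equal efficiency and no more adverse effects with mothers than with nurses. Randomisation supports that comparison in the 130 infants allocated, not in whoever completed. When a quarter are left out, the comparison is protected only if the reasons for leaving are unrelated to arm and outcome. The text does not show that. Similar numbers lost do not mean similar infants lost, because in one arm the mother must learn and deliver the procedure and in the other a nurse delivers it.

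A second, smaller gap concerns safety. The limits in the exclusion paragraph begin where the bands in the adverse-event outcome end. An event during study stimulation can arise only after allocation. An event during feeding may also do so, since at enrolment the infants were on tube feeds ("All these neonates were haemodynamically stable, established gavage feed"). If any infant was removed under that wording, the more severe events would have no stated place in the comparison that tests the safety hypothesis.

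**Working it through.** **1. Flow (Results; Sample size; Table 3)**
- 142 - 12 = 130 randomised, 65 + 65. The 12 are 2 + 1 + 1 + 8.
- Never stimulated: 130 - 107 = 23. Stimulated but not completing: 107 - 97 = 10.
- Omitted: 65 - 49 = 16 (24.6%) and 65 - 48 = 17 (26.2%), together 33/130 = 25.4%. Analysed: 97/130 = 74.6%.
- Difference in loss: 16/65 - 17/65 = -1.5 points (95% CI -16.3 to +13.3).

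Intervals here and below are Newcombe intervals for a difference of two proportions.

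**2. Do the printed results use 49 and 48?** The percentages in Table 3 are shares of the two-arm total (36/67 = 53.7%; 35/71 = 49.3%), so I work from the counts. One-sided Fisher exact tests reproduce the printed p-values:
- Adverse events D1, 36/49 v 31/48: 0.234 (printed 0.234).
- Level 4 at D14, 35/49 v 36/48: 0.434 (printed 0.434).

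The comparisons were therefore made on completers.

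**3. Level 4 at D14: how much depends on the 33?** Difference = experimental minus control.

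| Set | Experimental | Control | Difference, points (95% CI) |
|---|---|---|---|
| Completers | 35/49 (71.4%) | 36/48 (75.0%) | -3.6 (-20.7 to +13.9) |
| All 130, omitted = not achieved | 35/65 (53.8%) | 36/65 (55.4%) | -1.5 (-18.1 to +15.2) |
| Limit against mothers | 35/65 | (36 + 17)/65 = 53/65 | -27.7 |
| Limit in favour of mothers | (35 + 16)/65 = 51/65 | 36/65 | +23.1 |

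Counting the omitted as not achieved moves the difference towards zero. In a trial that hopes to show sameness this is not a conservative choice on its own, which is why the limits belong beside it.

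A caveat on the all-130 rows: the Primary Outcome Measure counts days from stimulation. The 23 never-stimulated infants therefore have no D14, and their status is a convention.

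**4. Adverse events on D1.** Completers: 36/49 - 31/48 = +8.9 points (-9.3 to +26.4). Only the 107 stimulated infants can have a D1. The arms of the 10 who did not complete are not in the text, so I searched every split of the 10:
- Lowest: all 10 experimental, none with an event: 36/59 - 31/48 = -3.6.
- Highest: all 10 control, none with an event: 36/49 - 31/58 = +20.0.

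This assumes all 10 reached D1, which the text does not say.

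**5. The safety passages side by side**

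| Item | Exclusion paragraph | Adverse-event outcome |
|---|---|---|
| High HR | above 200 | 180-200 |
| Low HR | below 100 | 120-100 |
| RR | above 70 | 60-70 |
| Choking, aspiration, apnea | listed | not listed |
| Consequence | infant excluded | event monitored |

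The intervention section gives a third consequence, stopping the feed. The start also differs: the arm description lists stimulation on T1 and T2 before D1, while the Primary Outcome Measure treats D1 as the commencement of stimulation and the first day of enrolment.

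**The case against.** **Losses are balanced and the analysed population is disclosed.** Both are true: 16 v 17, with 49 and 48 printed in every table. This removes any charge of unequal attrition or concealment. It does not supply an all-randomised comparison or show that the reasons for loss were alike.

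**Figure 1 may give the reasons.** It may, and its absence here is no fault of the plan. A flow diagram still cannot provide a missing-data method.

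**The extreme limits are implausible.** They put every omitted infant in one arm at one extreme and every one in the other arm at the opposite extreme. They show what the data leave open, nothing more.

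**The never-stimulated infants cannot be scored on the stated outcomes.** This stands. It rules out a D1 adverse-event range for all 130. It also means that a clock started at randomisation gives a different outcome from the one defined, and could add waiting time unrelated to who gave the stimulation.

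**The exclusion sentence sits among eligibility criteria.** A reader might infer that infants with severe events were dropped after randomisation and a safety signal lost. The documents do not support that. No such removal is reported, the in-trial response described is stopping the feed, and the adverse-event list is worded openly and said to cover every neonate. Nor can the opposite be concluded from the 12 infants left out before allocation. None of the reasons named is such an event, but that list is open too: "8 cases that did not meet the inclusion criteria due to different reasons such as syndromic features".

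**Conclusion.** The main point holds and must be fixed. A quarter of those randomised are missing from every outcome comparison, and no analysis or method addresses them. The conclusion of comparable results applies to the 97 completers. Even there a non-significant test does not show similarity: the Level 4 interval runs from -20.7 to +13.9 points. Across all 130 the point difference could lie anywhere from -27.7 to +23.1.

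A reader might go further and infer that the completer analysis is biased, or biased in favour of mothers. The documents do not support that: losses are near-equal in number, the text gives no reasons for them, and the direction of any bias is unknown.

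The safety point is secondary. It supports reconciling the passages and reporting a count by arm. The effect of the exclusion wording may be nil, and no figure for it can be derived. These conclusions assume that the flow counts are correct and that the omitted infants' outcomes are wholly unobserved.

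**What to change.** Keep the 97-infant analysis, label it as completers, and add the following by randomised arm.

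1. **Level 4 in all 130**, with unobserved counted as not achieved and the extreme limits beside it. State that the 23 never-stimulated infants have no D14 as the outcome is defined. Either anchor status to a calendar day from randomisation, or say that non-achievement is a convention.
2. **Supplementary time to full oral feed from randomisation**, using chart data where they exist and censoring at last observation. Label it as a different time origin from the defined primary outcome, not comparable with the reported medians of 10 v 9 days. State that infants without follow-up add little and that censoring at an event may be informative.
3. **Reasons for the 33 by arm**, if Figure 1 does not give them.
4. **Conclusion limited** to the intervals and bounds obtained.
5. **Safety.** Reconcile the exclusion paragraph, the intervention section and the adverse-event outcome, including whether T1 or D1 starts stimulation and monitoring, without changing any clinical rule. Report by arm how many infants, if any, were removed after randomisation under the exclusion wording (zero if none). Count such events by arm in the 107 stimulated and, where recorded, in all randomised infants.

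The cost is two added analyses, one event count and clarifying text. Proforma entries were made at D1 to D14, so outcomes may be unrecoverable for infants who never started or left early. Results may be less precise or less favourable.

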- Hemodynamically significant patent ductus arteriosus (HsPDA) diagnosed by echocardiography
- Necrotizing enterocolitis (NEC) diagnosed using modified Bell's scoring (stage 1)
- Feeding intolerance diagnosed as aspirates > 20% of previous feed ± abdominal distension of > 2cm from base line
- Sepsis (leukocytosis or leukopenia or ANC<150 along with raised CRP and platelets <100 and or positive blood culture)
- Seizures
- Discharge weight in kg
- Duration of stay in NICU in days
- Neonatal feeding characteristics at time of enrollment in study include
 - Postmenstrual age (PMA) measured in weeks
 - Chronological age (ChA) measured in weeks
 - Time/duration to achieve full gavage/tube feed measured in days
 - Daily milk intake (ml/kg/day) when sensory motor stimulation was started
 - Volume of feed prescribed for each feed (ml)

The **outcome** measured were documented daily twice a day (11.00 and 17.00 hrs) until achievement of full oral feed. Full oral feed was volume of 120-140ml/kg/day taken orally. However, to make calculations concise, for both groups, all outcome parameters were documented on proforma for fixed time (11.00 am) for D1, D2, D3, D5, D7 and D14.

- Primary Outcome Measure
 - Transition time to full oral feeding is the time interval between commencement of perioral sensory stimulation on D1 to establishment of full oral feed in both groups. It was done daily till 14th day of perioral sensory motor stimulation. Transition time to full oral feeding was the day at which baby was able to take oral feed of volume of 120-140ml/kg/day.
 - Improvement (change) in efficiency oral feed establishment in terms of amount and time. It was classified into four levels depending upon the level of maturity in ascending order as follows:
 - Level 1: PRO < 30% and RT < 1.5 ml/min
 - Level 2: PRO < 30% and RT ≥ 1.5 ml/min
 - Level 3: PRO ≥ 30% and RT < 1.5 ml/min
 - Level 4: PRO ≥ 30% and RT ≥ 1.5 ml/min

For our RCT, efficacy was measured as the achievement of L4 for the intervention group vs the control group.

- Adverse outcome monitoring was done for every neonate from first day of enrollment in study (D1) till establishment of full oral feed (by D14 expected). These include non-life threatening adverse events including cough, tachycardia HR 180-200/min, bradycardia HR120 - 100/min, , tachypnea RR 60 - 70/min while maintaining SpO2 of >90% at room air
- Secondary Outcome Measure:
 - Total volume (TV) taken during each feed

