Seizures ^a	7 (58.3%)	5 (41.7%)	0.394		
M A T E R N A L	Age ^b	29 (26 - 32)	30 (26.5 – 33)	0.138	
	Gravidity ^a	Primigravida	20 (43.5%)	26 (56.5%)	0.350
		2-3	22 (59.5%)	15 (40.5%)	
		≥ 4	7 (50.0%)	7 (50.0%)	
	Education ^a	Uneducated	2 (50.0%)	2 (50.0%)	0.699
		Primary	11 (52.4%)	10 (47.6)	
		Secondary	15 (42.9%)	20 (57.1%)	
		Higher	21 (56.8%)	16 (43.2%)	
	Previous preterm (yes) ^a	42 (52.5%)	38 (47.5%)	0.281	
	Job status (Housewife) ^a	29 (48.3%)	31 (51.7%)	0.368	
Hypertensive disorder ^a	29 (47.5%)	32 (52.5%)	0.290		
DM ^a	17 (50.0%)	17 (50.0%)	0.555		
Anemia ^a	25 (54.3%)	21 (45.7%)	0.304		

Table 2 : Feeding characteristics

Feeding characteristics	Experimental group (n=49)	Control group (n = 48)	p-value
PMA at enrollment (week)	32 (31 – 33)	32 (31 – 33)	0.787
ChA at enrollment (days)	13 (6 – 14)	9 (7 – 16)	0.925
Time to full gavage feed (days)	7 (5.5 – 13.5)	7 (6 – 14)	0.726
Discharge weight (kg)	1.48 (1.42 – 1.66)	1.48 (1.43 – 1.75)	0.698
Weight at enrollment (kg)	1.35 (1.25 – 1.54)	1.35 (1.21 – 1.60)	0.610
Duration of stay in NICU (days)	21 (15 – 29.5)	30 (16 – 30.75)	0.848
Milk Feed (ml/kg/day)			
Milk feed D1	120 (120 – 120)	120 (120 – 120)	0.302
Milk feed D2	120 (120 – 140)	120 (120 – 140)	0.871
Milk feed D3	140 (140 – 140)	140 (140 – 157.50)	0.109
Milk feed D5	150 (150 – 160)	160 (150 – 160)	0.361
Milk feed D7	160 (160 – 160)	160 (160 – 160)	0.184
Milk feed D14	160 (160 – 180)	160 (160 – 180)	0.758
Volume of feed prescribed (ml/feed)			
Volume prescribed D1	14 (12 – 15.5)	14 (12 – 16)	0.670
Volume prescribed D2	14 (12 – 17.5)	12.5 (12.25 – 19)	0.825
Volume prescribed D3	16 (14 – 17.5)	14 (14 – 20)	0.569
Volume prescribed D5	17 (15 – 19)	17 (15 – 21)	0.758
Volume prescribed D7	18 (16 – 20.5)	18 (16 – 22)	0.614
Volume prescribed D14	18 (16 – 22)	18 (16 – 24)	0.933

Table 3 : Study outcome

Outcome		Experimental gp (n=49)	Control gp (n=48)	p-value
Time to full oral feed (days)		10 (7 – 13)	9 (7 – 13)	0.531
Adverse events	D1	36 (53.7%)	31 (46.3%)	0.234
	D2	14 (50.0%)	14 (50.0%)	0.563
	D3	12 (50.0%)	12 (50.0%)	0.570
	D5	2 (100%)	0 (00%)	0.253
	D7 & 14	0 (00%)	0 (00%)	NA
L4 Efficacy on	D 1 -3	0 (00%)	0 (00%)	NA
	D5	12 (57.1%)	9 (42.9%)	0.331
	D7	16 (51.6%)	15 (48.4%)	0.528
	D14	35 (49.3%)	36 (50.7%)	0.434
Volume Taken Each feed	D1	2.0 (2.0 -7.0)	2.0 (2.0 -7.0)	0.803
	D2	5.0 (2.0 - 9.0)	3.0 (2.0 – 7.0)	0.558
	D3	7.0 (3.0 – 11)	4.0 (3.0 – 10.0)	0.540
	D5	8.0 (5.0 – 15)	6.5 (5.0 – 15)	0.521
	D7	9.0 (7.0 – 18)	7.5 (7.0 – 20)	0.951

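### L4 efficacy, a primary outcome, is tested as three separate single-feed proportions, with no single comparison of when L4 was reached and no confidence interval

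*Combined protocol and SAP*

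**What the plan says.** All of this is in the combined protocol and SAP.

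- **Definition.** Under Primary Outcome Measure, feeding efficiency is graded in four levels, the highest being "Level 4: PRO ≥ 30% and RT ≥ 1.5 ml/min". The plan then states: "For our RCT, efficacy was measured as the achievement of L4 for the intervention group vs the control group". No day is attached.
- **Recording.** Under Data Collection, outcomes were "documented daily twice a day (11.00 and 17.00 hrs) until achievement of full oral feed".
- **Thinning.** The next lines say that, to shorten the calculations, "all outcome parameters were documented on proforma for fixed time (11.00 am) for D1, D2, D3, D5, D7 and D14".
- **Method.** The Statistical analysis section gives Fisher or chi-square tests for categorical variables. It describes no time-to-event, grouped-time or repeated-measures method.
- **Result.** Table 3 has rows headed "L4 Efficacy on" for each day, each with its own p-value and no interval. The Results find no significant difference in time to full oral feeding, "adverse events, or the effectiveness observed during oral assessments", and call the arms' feeding skills comparable.

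**The concern.** Achieving a level is an event with a date, but Table 3 shows only how many infants were at the level at one feed on each of a few days. An infant at L4 from D8 and one first at L4 on D14 count the same. Most of the net rise in L4 falls between the last two readings, where the analysis has none.

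The trial hypothesises that mothers do as well as nurses. For such a claim, an analysis that is insensitive to delay leans towards the hoped-for answer. Three separate non-significant tests without an interval do not tell the reader how large a delay remains possible.

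**Working it through.** **1. Inputs (Table 3; n = 49 mothers, 48 nurses).** The printed percentages are shares of the row total (35/71 = 49.3%), so arm rates are recomputed.

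| Day | Mothers | Nurses | Printed p | One-sided Fisher | Two-sided Fisher |
|---|---|---|---|---|---|
| D5 | 12/49 = 24.5% | 9/48 = 18.8% | 0.331 | 0.3306 | 0.623 |
| D7 | 16/49 = 32.7% | 15/48 = 31.2% | 0.528 | 0.5278 | 1.000 |
| D14 | 35/49 = 71.4% | 36/48 = 75.0% | 0.434 | 0.4336 | 0.819 |

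The printed p-values are reproduced, but only as one-sided Fisher tests in the observed direction. That is a separate matter and does not affect this point.

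**2. Infants added after D7.** Mothers 35 − 16 = 19; nurses 36 − 15 = 21; together 40. This is 40/71 = 56% of those at L4 on D14 and 40/97 = 41% of all infants. It is a net count. If L4 can be lost, it is a minimum for infants at L4 on D14 but not at the D7 feed. Loss is plausible, since the SSB coordination counts fall from D5 to D7 in both arms (40 to 39 and 37 to 36).

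**3. What the L4 rows allow.** Suppose L4 is kept once reached. Both arms are below 50% on D7 and above it on D14, so both medians lie in D8–D14 and may differ by anything from −6 to +6 days with no cell changed.

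Extreme case: earlier infants on D5 and D7, the mothers' 19 on D14, the nurses' 21 on D8, and the rest counted as 14 days.
- Mothers: (12×5 + 4×7 + 19×14 + 14×14)/49 = 550/49 = 11.2 days.
- Nurses: (9×5 + 6×7 + 21×8 + 12×14)/48 = 423/48 = 8.8 days.
- Difference 2.4 days, z about 3.2. The printed p-values are identical. The log-rank p is 0.16, so a standard log-rank test would not recover even this.

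**4. What is partly visible.** Assume the nurses' curve is linear from D7 to D14: (75 − 31.25)/7 = 6.25 points per day. Delays of 2, 3 or 4 days in infants reaching L4 after D7, allowed to run past D14, lower the mothers' D14 rate to 62.5%, 56.3% or 50.0%. Two-sided Fisher power at D14 is then 21%, 44% or 69%. If earlier infants are delayed too, the D7 comparison has 29% power at 2 days and 77% at 3 days (normal approximation).

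The observed D14 difference is −3.6 points. Its standard error is √(0.714×0.286/49 + 0.75×0.25/48) = 0.090, so the 95% CI is −21.2 to +14.0. A 3-day delay of this kind (−18.75 points) is not excluded.

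**5. Power of a combined analysis (simulated, 49 v 48, control curve near 19%, 31% and 75% at D5, D7 and D14).**
- *Hazard ratio 0.6 throughout.* Fisher at D14 about 43%; D5, D7 and D14 taken jointly about 49%; complete daily dates about 51%. Nearly all the gain comes from combining readings, not from daily dating.
- *Part of that gain is Fisher's conservatism.* The mothers' D14 rate is 1 − 0.25^0.6 = 0.565 and the pooled rate 0.656. An uncorrected chi-square at D14 has power Φ[(0.185 − 1.96×0.0964)/0.0945], about 48%.
- *Arms equal on D5, D7 and D14, with the mothers' later infants all on D12–D14.* Fisher 3–4% on each day. With complete daily dates the log-rank has about 13–17%, falling to about 9% once records stop at full oral feed.

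**The case against.** The strongest reply has four parts.

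- **The schedule is disclosed, and a proportion at L4 on fixed days is one fair reading of achievement.** This stands in part. Time to first L4 is a different estimand: it credits one good feed even if the level is then lost. But the plan names no day, so three unlinked tests do not settle the question either.
- **Timing is already measured.** Transition time to full oral feed was followed daily to day 14 and is similar: 10 (7–13) v 9 (7–13) days, p=0.531. The components of L4 also agree at both ends of the window: median RT 1.0 v 1.0 on D7 and 1.6 v 1.6 on D14; PRO 39 v 39 and 56 v 55.8. This stands, and makes a hidden delay of several days less plausible. It does not date L4, because full oral feed is a daily volume while L4 is proficiency and rate at one feed, listed as its own primary measure.
- **The daily records are incomplete.** They run only until full oral feed, with a lower quartile of 7 days in both arms, so many infants have no daily record for much of D8–D13. This stands. A reader might infer that every infant's date can be recovered, and the documents do not support that.
- **The remedy has little power for a delay confined to D8–D14.** This stands, and is why the fix rests on an estimate with an interval rather than on another p-value.

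A reader might also infer that a delay in the mothers' arm cannot be seen at all, or that one is being concealed. The first is true only of a delay wholly inside D8–D14. For the second, the documents give no evidence.

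**Conclusion.** The point holds for the L4 outcome, within limits. L4 achievement is judged from separate single-feed proportions on D5, D7 and D14, with no one comparison of when it was reached and no interval. A net 40 of 71 D14 achievers (56%) are dated only to a seven-day window. A delay confined to that window would not alter the L4 rows; one that starts earlier or runs past D14 is partly visible.

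This rests on two assumptions. The first is that L4, once reached, is kept; otherwise 40 is a minimum. The second is that the Table 3 rows show status at the 11:00 feed. That follows from the recording schedule and the falling SSB counts, but the table does not label it.

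The finding does not overturn the result or show that the mothers' arm was slower, and the trial is not without timing data. It shows that the effectiveness conclusion goes further than the L4 analysis supports.

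**What to change.** Replace the three separate tests with one analysis of time to first recorded L4, up to D14.

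- Use the twice-daily records where they exist. Where an infant's records stop at full oral feed before L4, treat the time as interval-censored up to the next scheduled reading. Censor at D14 infants who never reach L4.
- If the daily records cannot be retrieved, say so and run a grouped-time analysis of D5, D7 and D14 together.
- Fit an interval-censored or discrete-time model, not a standard log-rank or Cox analysis.
- Report the between-arm difference, for example in restricted mean days to D14, with a 95% confidence interval. State that one feed at L4 counts as reaching it.
- Keep the daily counts as description, with arm denominators.
- Limit the effectiveness statement to the delays that the interval excludes.

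The cost is some data extraction and one further analysis, with no new infants or assessments. The downside is that dates are lost where records stop at full oral feed, which widens the interval. The gain in power is modest, as shown above. What is gained is a single estimate that answers the stated question.
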